## 10. Statistical Considerations

### 10.1. Sample Size Determination

Over the course of the study, approximately 60 participants will be randomized in a 1:1 ratio to receive one of the following: 120mg alvelestat (MPH966) BID or placebo. Randomization will be stratified by study site and by AAT genotype/phenotype.

The study will be powered for within-individual change in plasma desmosine/isodesmosine as the primary endpoint at Week 12 compared to baseline. A sample size of 30 participants in the MPH966 treatment group will give us >90% power to detect a 15% mean decrease of plasma DES from baseline to 12 weeks follow-up in patients treated with MPH966 (within subject change) using a two-sided paired t-test at  $\alpha=0.05$ . This 15% mean decrease has been observed in trials of standard dose augmentation versus placebo. A recent study of double dose versus single dose augmentation revealed a within subject decrease in plasma DES from 0.42 +/-0.03 ng/ml to 0.38 +/- 0.03 ng/ml. We will have 80% power to detect a comparable difference in DES in those who have alvelestat added to augmentation.

For comparing the mean change in DES between the two groups (placebo vs. MPH966), and assuming that there is no placebo effect over 12 weeks, a two-sided two sample t-test at  $\alpha=0.05$  with a sample size of 60 (30 per group) reveals that we will have 82% power to detect a 15% difference in mean change in plasma DES.

Other secondary endpoints (BAL and sputum DES, other serum, sputum and BAL inflammatory markers, patient-reported outcomes, and pulmonary function) will be examined within and between group with paired t-tests or mixed effect modeling as appropriate.

We will also examine the association between DES at baseline and response to treatment as measured by change in pulmonary function (FEV1) over 12 weeks within the MPH966 treatment group. With a sample size of 30, we will have 80% power to detect a 0.12 regression correlation coefficient of DES at baseline in predicting the change of FEV1 over 12 weeks when the standard deviation of DES is 0.10 and  $\alpha=0.05$ .

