### 10.3. Statistical Analyses

The statistical analysis will be performed using SAS® version 9.4 or higher. The main population for efficacy analysis will be the Full Analysis Set; supportive analyses will also be performed using the Per-Protocol Set.

Continuous data will be presented using descriptive summaries (e.g., mean, standard deviation, minimum, maximum, median, lower quartile, and upper quartile). Categorical variables will be presented by the number of observations and relative (%) frequency.

Unless otherwise stated, baseline value for any variable will be the last value taken prior to the first dose of study medication.

Unless otherwise stated, all statistical tests will be 2-sided and conducted at the 5% level. All presented confidence intervals will be 2-sided 95% confidence intervals.

The Statistical Analysis Plan (SAP) will be developed and finalized before database lock and will describe the selection of participants to be included in the analyses and procedures for accounting for missing, unused, and spurious data. Below is a summary of planned statistical analyses of the primary and secondary endpoints.

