# 3.5.3 Sample Size

Over the course of the study, target enrolment is 66 with the goal of 60 completers. Participants will be randomized in a 1:1 ratio to receive one of the following: 120mg Alvelestat (MPH966) BID or placebo. Randomization will be stratified by AAT genotype/phenotype.

The study will be powered for within-individual change in plasma desmosine/isodesmosine (DES) as the primary endpoint at Week 12 compared to baseline. A sample size of 30 participants in the MPH966 treatment group will give us >90% power to detect a 15% mean decrease of plasma DES from baseline to 12 weeks follow-up in patients treated with MPH966 (within subject change) using a two-sided paired t-test at  $\alpha$ =0.05. The calculation is based on an assumed correlation value of 0.5, baseline mean DES value of 0.466 and standard deviation of 0.09. This 15% mean decrease has been observed in trials of standard dose augmentation versus placebo (Ma S, 2013). A recent study of double dose versus single dose augmentation revealed a within subject decrease in plasma DES from 0.42 +/-0.03 ng/ml to 0.38 +/- 0.03 ng/ml (Campos MA, 2019). We will have >99% power to detect a comparable difference in DES in those who have Alvelestat added to augmentation if we assume their observed SD=0.03 and 85% power if we double their assumed SD, i.e., SD=0.06. Power will not be enough (~50%) to detect this difference if we use our original SD value of 0.9.

For comparing the mean change in DES between the two groups (placebo vs. MPH966), and assuming that there is no placebo effect over 12 weeks, a two-sided two sample t-test at  $\alpha$ =0.05 with a sample size of 60 (30 per group) reveals that we will have 82% power to detect a 15% difference in mean change in plasma DES.

By including a 10% attrition rate over 12 weeks, the required sample size is inflated to 66 (33 per group) to achieve the estimated powers. If we observe attrition rate less than we expected, we will have more statistical power to detect the expected differences. As one interim analysis will be conducted only for safety concerns (see Data Safety and Monitoring Plan), no adjustments to the Type I error are considered for estimating statistical powers.

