# 10 Changes from Analysis Planned in the Protocol

In Version 1.3 of the protocol, augmentation therapy was removed from the list of not allowed treatment. Sample size calculation was revised but sample size remained the same. Also, stratified analyses by augmentation therapy will be performed.

Due to the risk during the COVID pandemic, spirometry as well as sputum and BAL collections were changed to optional. Consequently, all analyses using spirometry, sputum biomarkers, and BAL biomarker outcomes and data will no longer be performed in this study.

Primary analysis in the protocol is based on ANCOVA with outcome being the percent change at Week 12 from baseline. However, to minimize the effect of missing data and to maximize the information from all visits, the primary analysis is now based on fitting a mixed model using change from baseline at all available follow-up visits as outcome with the assumption of missing at random for missing data.

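### The 80% power that Protocol 10.1 claims for a 0.12 coefficient of baseline DES on FEV1 change does not follow from its stated inputs

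*Protocol*

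**What the plan says.** Protocol section 10.1 adds to the power statements for DES itself a calculation for a different question: whether baseline DES predicts response, measured as "change in pulmonary function (FEV1) over 12 weeks within the MPH966 treatment group". For a sample of 30 it reads: "we will have 80% power to detect a 0.12 regression correlation coefficient of DES at baseline". The condition attached is "when the standard deviation of DES is 0.10", with alpha 0.05. No SD or unit is given for the FEV1 change. Sidedness is not stated in the sentence, but the general rule in Protocol section 10.3 is that "all statistical tests will be 2-sided and conducted at the 5% level".

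SAP section 3.5.3 repeats the DES power statements, now with a "baseline mean DES value of 0.466 and standard deviation of 0.09", and leaves the FEV1 calculation out. SAP section 10 says that, because spirometry became optional during the pandemic, "all analyses using spirometry, sputum biomarkers, and BAL biomarker outcomes and data will no longer be performed in this study".

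**The concern.** A correlation of 0.12 is weak, and 30 patients cannot detect a weak correlation with 80% power. The sentence therefore conveys far more sensitivity than a sample of this size can have. If 0.12 is instead a slope, the input that decides the power is missing and the figure cannot be checked.

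What is at stake is interpretation. If the association were examined and found null, a reader relying on section 10.1 could take that as adequately powered evidence that baseline DES does not predict FEV1 response. The sentence gives no basis for that conclusion.

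**Working it through.** **Inputs from the documents.** n = 30 (active arm), coefficient 0.12, SD of baseline DES 0.10 and alpha 0.05 (all Protocol 10.1); two-sided testing (Protocol 10.3). The alternative SD of DES, 0.09, is from SAP 3.5.3. The residual SD and unit of the FEV1 change are in neither document.

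**1. Trying to reproduce 80%, with 0.12 as a correlation.**
- Fisher z: atanh(0.12) × √(30 − 3) = 0.1206 × 5.196 = 0.627. Power = Φ(0.627 − 1.960) + Φ(−0.627 − 1.960) = 0.091 + 0.005 = **9.6%**.
- Noncentral t test of the slope, noncentrality r/√(1 − r²) × √n with 28 df: 9.8%. Simulation with 100,000 replicates: 9.5%.
- Other variants also miss 80%:

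| Variant | Power |
|---|---|
| r = 0.12, n = 30, one-sided | 15–16% |
| r = 0.12, n = 33, two-sided | about 10% |
| r = 0.12, n = 60, two-sided | about 15% |
| r = 0.12, n = 66, two-sided | about 16% |
| 0.12 as R², n = 30, two-sided / one-sided | 47–50% / 59–63% |
| 0.12 as f², n = 30, two-sided / one-sided | 42–45% / 55–58% |

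- Sample size for 80% power at r = 0.12: ((1.960 + 0.842)/0.1206)² + 3, about 543 patients.

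**2. 0.12 as a slope per unit of DES.** Noncentrality = slope × SD of DES × √n / residual SD. With 28 df and two-sided 5%, 80% power needs a noncentrality of 2.902.
- Required residual SD = 0.12 × 0.10 × √30 / 2.902 = 0.0657/2.902 = **0.0226**. With √29 in place of √30 it is 0.0223. With SD of DES 0.09 (and √30) it is 0.0204.
- If FEV1 is in litres, 0.022 to 0.023 is 22 to 23 mL.
- Power at other residual SDs, which are assumptions because the documents give none:

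| Assumed residual SD of FEV1 change | Noncentrality (√30) | Power (√29 to √30) |
|---|---|---|
| 50 mL | 1.31 | 24–25% |
| 100 mL | 0.66 | 10% |
| 150 mL | 0.44 | 7% |
| 200 mL | 0.33 | 6% |

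**3. 0.12 as litres per 1 SD of DES.** The text does not say this. Required residual SD = 0.12 × √30 / 2.902 = 0.226 L (0.223 L with √29), so about 0.22 to 0.23 L.

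**4. What 80% power at n = 30 means on each of these readings.** A two-sided test of one predictor depends only on the correlation and n.
- Fisher z: tanh((1.960 + 0.842)/√27) = tanh(0.539) = **0.49**.
- Noncentral t: 2.902/√30 = 0.530, and 0.530/√(1 + 0.530²) = **0.47**.
- Cross-check from step 2: 0.012/√(0.0226² + 0.012²) = 0.012/0.0256 = 0.47.

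**The case against.** The strongest reply is that a correlation was never meant. A correlation power calculation does not use the SD of the predictor, whereas a slope calculation does, and the sentence gives one. On that reading no arithmetic error is shown: the residual SD was left out and the term is loose. This stands. A reader might infer from the 10% figure that the stated power is wrong by a factor of eight, but that holds only if 0.12 is a correlation.

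A reader might also infer that the slope reading needs an implausibly small residual SD. The documents do not support that step. They give no SD for FEV1 change, so 22 to 23 mL can be compared only with assumed values. The scale is open too: per 1 SD of DES, the requirement rises to 0.22 to 0.23 L. Against that scale, the SD of DES would then serve only to define the unit and would not enter the power, so its presence points to raw units.

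The other reply is that nothing depends on the sentence. It does not drive the sample size, and this regression is not among the endpoints or planned efficacy analyses of either document, nor in the SAP's output lists. That also stands. SAP 4.4, 8.3 and 14.2 still list some spirometry results, and a reader might infer that the DES–FEV1 analysis therefore survives. It does not follow. Those entries concern spirometry values and their change from baseline, and the correlations in SAP 8.3 relate biomarkers to drug concentrations and PK parameters. Whether those entries agree with SAP section 10 is a separate question.

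**Conclusion.** The concern holds as a matter of statement: the inputs in Protocol 10.1 do not yield 80% power for a coefficient of 0.12. Under the sentence's own term, correlation, power is about 10%. Under the slope reading that its inputs suggest, the claim cannot be verified without an FEV1 unit and a residual SD, and it is met only at a residual SD of about 0.022 to 0.023. The firm result, which needs no assumption about FEV1 variability, is that 30 patients give 80% power for a correlation of about 0.47 to 0.49 at a two-sided 5% level. That is a moderately strong association, not the weak one that the wording conveys.

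Impact is low. The randomized number, the primary analysis and the error rate are unaffected, and the SAP has dropped the calculation.

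**What to change.** Delete the sentence from Protocol 10.1. SAP 3.5.3 already omits the calculation, and SAP section 10 says spirometry analyses will not be performed.

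If the association is still to be examined, replace the sentence with a statement that 30 treated patients give 80% power, two-sided 5%, for a correlation of about 0.47 to 0.49 between baseline DES and 12-week FEV1 change, and label the analysis descriptive. If a slope was intended, also give its unit, the FEV1 unit, and the residual SD with its source.

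The cost is one sentence and a less favourable figure. No design or primary-analysis change follows.

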### 10.2. Populations for Analyses

For purposes of analysis, the following populations are defined:

Population	Description
Enrolled Set	The Enrolled Set will include all participants who sign the ICF.
Randomized Set	The Randomized Set will include all subjects who signed the ICF and were subsequently randomized into the study, regardless of study treatment administration.
Full Analysis Set	The Full Analysis Set will serve as the primary population for the analysis of efficacy and will consist of all randomized subjects who took at least 1 dose of double-blind study treatment and have at least 1 evaluable change from baseline in plasma desmosine/isodesmosine levels. Subjects will be analyzed according to randomized treatment.

Population	Description
Per-Protocol Set	The Per-Protocol Set includes all participants from the Full Analysis Set who have been treated according to the protocol and fulfil the following criteria: 
 
1. All inclusion/exclusion criteria satisfied
 
2. Absence of relevant protocol violations with respect to factors likely to affect the efficacy of treatment where the nature of protocol violation will be defined before breaking the blind
 
3. Adequate study medication compliance, which will be determined before breaking the blind
 
 Subjects will be analysed according to randomized treatment.
Safety Set	All randomized participants who take at least 1 dose of study treatment. Participants will be analysed according to randomized treatment.
PK Set	The PK Set will include all participants in the Safety Set who have at least 1 evaluable serum concentration.

### 10.3. Statistical Analyses

The statistical analysis will be performed using SAS® version 9.4 or higher. The main population for efficacy analysis will be the Full Analysis Set; supportive analyses will also be performed using the Per-Protocol Set.

Continuous data will be presented using descriptive summaries (e.g., mean, standard deviation, minimum, maximum, median, lower quartile, and upper quartile). Categorical variables will be presented by the number of observations and relative (%) frequency.

Unless otherwise stated, baseline value for any variable will be the last value taken prior to the first dose of study medication.

Unless otherwise stated, all statistical tests will be 2-sided and conducted at the 5% level. All presented confidence intervals will be 2-sided 95% confidence intervals.

The Statistical Analysis Plan (SAP) will be developed and finalized before database lock and will describe the selection of participants to be included in the analyses and procedures for accounting for missing, unused, and spurious data. Below is a summary of planned statistical analyses of the primary and secondary endpoints.

#### 10.3.1. Efficacy Analyses

Endpoint	Statistical Analysis Methods
Primary	Within individual % change from baseline in plasma desmosine/isodesmosine levels at 12 weeks will be calculated. An analysis of covariance (ANCOVA) model with baseline plasma desmosine/isodesmosine levels as a covariate and treatment and sputum strata as factors will be used to generate least squared means and least squared mean differences between treatment groups.
Secondary	The biomarker correlation analysis will be done using stepwise approach: The parameters in BAL, sputum, and blood during treatment will be compared to the baseline values for active and placebo patients separately to evaluate natural variability of the markers.  The time-matched biomarker values will be compared between placebo and active groups to assess the differences outside natural variability and time to significant change for the responsive biomarkers.

Endpoint	Statistical Analysis Methods
	
Multiple models, including non-parametric models, will be considered within this frame incorporating different covariates and data transformations. PD parameters such as area under the effect-time curve will also be considered.
 
Principal component multifactorial analysis and/or cluster analysis may be employed to simplify the comparison and to explore the treatment effect. Decisions will be made on review of data and prior to database lock.
 
Correlation of select biomarkers shown to be responsive to treatment with time-matched drug concentrations and PK parameters, if available, may be used to evaluate exposure-response relationship.

Exploratory	
Observed values and change from baseline in FEV1, FVC, FEV1/FVC (total and percent predicted) and maximal mid-expiratory flow will be presented by treatment group and study visit. Change from baseline at Week 12 will be analysed using an ANCOVA model.
 
Observed values and change from baseline for the total and component scores of the SGRQ-C will be presented by treatment group and study visit. Change from baseline in total score at Week 12 will be analysed using an ANCOVA model.
 
Correlation of select biomarkers shown to be responsive to treatment with time-matched drug concentrations and PK parameters, if available, will be used to evaluate exposure-response relationship.

### 10.3.2. Safety Analyses

All safety analyses will be performed on the Safety Set.

Endpoint	Statistical Analysis Methods
Primary	
AEs will be coded using the Medical Dictionary for Regulatory Activities (MedDRA). Summaries will be by system organ class and preferred term. Treatment-emergent AEs are defined as any AE occurring or worsening on or after the first dose of study medication. If a participant experiences the same preferred term multiple times, the event will be counted only once overall and by the greatest severity.
 
The frequency and incidence of treatment-emergent AEs will be presented by system organ class and preferred term for each treatment group (number and percentage of participants experiencing at least 1 AE per preferred term as well as the number of observed events per preferred term). Separate tables will be presented by severity and by relationship. All AEs will be presented in full in a comprehensive listing including participant number, treatment regimen, severity, seriousness, action taken, outcome, relationship to treatment, onset/stop, and duration. Details of SAEs and AEs leading to withdrawal will be listed separately.
 
Adverse Events of Special Interest AESIs, including liver function abnormalities, ECG/cardiac events, infections, and neutropenia, will be tabulated and summarized by treatment group and overall.

Secondary	Vital Signs

Endpoint	Statistical Analysis Methods
	
Vital signs will be summarized as observed values and change from baseline by treatment group and overall.
 
Physical Examination Physical examination results will be listed by subject ID and body system.
 
ECG ECG parameters will be summarized as observed values and change from baseline by treatment group and study visit.
 
Abnormal findings (“normal”, “abnormal, not clinically significant”, and “abnormal, clinically significant”) will be summarized by the number and percentage within each category, and change from baseline will be summarized by shift tables.
 
Clinical Laboratory Laboratory parameters will be summarized as observed values and change from baseline by treatment group and study visit.
 
Values outside the normal range will be summarized by the number and percentage within each category, and change from baseline will be summarized by shift tables.
 
Safety and PK Relationships The safety correlation analysis with drug concentration may be done for the safety parameters shown to be sensitive to alvelestat exposure. The comparison of exposure will be done between groups with non-clinically significant changes and clinically significant changes in safety parameters using graphic and statistical methods where data allow.

Exploratory	The details will be described in the SAP finalized before database lock.

### 10.3.3. Other Analyses

PK, PD, and biomarker exploratory analyses will be described in the SAP finalized before database lock.

### 10.3.4. Interim Analyses

No interim analysis for efficacy is planned for this study. An interim safety analysis will be conducted when 30 subjects have completed the study.

**12. Appendices**

**Appendix 1: Abbreviations, Trademarks & Glossary**

Abbreviation	Description
AAT	Alpha-1 antitrypsin
AATD	Alpha-1 antitrypsin deficiency
A<math>\alpha</math>-Val360	Fragment from neutrophil elastase cleavage of elastin at A $\alpha$ -Val360 site
AcPGP	Acetylated Proline-Glycine-Proline
AE	Adverse event
AESI	Adverse event of special interest
ALT	Alanine aminotransferase
ANCOVA	Analysis of covariance
AST	Aspartate aminotransferase
AUC	Area under the curve
BAL	Bronchoalveolar lavage
bid	Twice (2 times) a day
C1M	MMP-derived collagen type I breakdown fragment
C6M	MMP-derived collagen type VI breakdown fragment
CAT	COPD assessment test
Cat g	Cathepsin G
CF	Cystic fibrosis
CFR	United States Code of Federal Regulations
CMP	Complete metabolic profile
CMV	Cytomegalovirus
CONSORT	Consolidated Standards of Reporting Trials
COPD	Chronic obstructive pulmonary disease
CRF	Case report form
CRO	Clinical Research Organization
CT	Computerized or computed tomography

CYP2C9	Cytochrome P450 2C9
DCC	Data Coordinating Center
DES	Desmosine
dL	Decilitre
DSMB	Data Safety Monitoring Board
EBV	Epstein-Barr virus
ECG	Electrocardiogram
eCRF	Electronic case report form
EL-CG	Elastin degradation mediated by Cathepsin G
EL-NE	Elastin degradation mediated by NE
EL-P3	Elastin like polypeptide 3
EOT	End of treatment
EP-3	Elastin peptide 3
FEV1	Forced expiratory volume in 1 second
FEV1/FVC	Forced expiratory volume in 1 second divided by the forced vital capacity
FVC	Forced vital capacity
FIB-4	Fibrosis-4
FU	Follow-up
FVC	Forced vital capacity
g	Gram
GCP	Good Clinical Practice
h	Hour
hCG	Human chorionic gonadotropin
HIV	Human immunodeficiency virus
hsCRP	High-sensitivity C-reactive protein
HRT	Hormone replacement therapy

HSV	Herpes simplex virus
Hy's Law	a rule of thumb that a patient is at high risk of a fatal drug-induced liver injury (DILI) if given a medication that causes hepatocellular injury (not cholestatic injury) with jaundice
IC50	the concentration of an inhibitor where the response (or binding) is reduced by half
ICF	Informed consent form
ICH	International Conference on Harmonization
IEC	Independent Ethics Committee
IL-1<math>\beta</math>	Interleukin 1 beta
IL-6	interleukin-6
IL-8	interleukin-8
IND	Investigational new drug
INR	International normalized ratio
IRB	Institutional Review Board
IWRS	Interactive web response system
Ki	Inhibitory constant
kPa	kiloPascal, a unit of force
LSM	Liver stiffness measurement
LTB4	Leukotriene b4
MedDRA	Medical Dictionary for Regulatory Activities
mGy	milliGray, a unit of radiation
mg/dL	Milligrams per decilitre
mIU	Milli International Units
MMP	Matrix metalloproteinase
MMRC	Modified medical research council
MOP	Methods of procedures
MPO	Myeloperoxidase

MS	Millisecond
mSV	milliSever
NCATS	National Center for Advancing Translational Science
NCT	National Clinical Trial
NE	Neutrophil elastase
NIH	National Institutes of Health
NOAEL	No observed adverse effect level
NSAID	Non-steroidal anti-inflammatory drug
Pa	Pascal
PD	Pharmacodynamics
PI	Principal investigator
Pi*ZZ	Alpha-1 ZZ genotype
Pi*SZ	Alpha-1 SZ genotype
Pi*Null, Null	Alpha-1 Null genotype
PGP	P-glycoprotein
PK	Pharmacokinetics
PR	time from the onset of the P wave to the start of the QRS complex on ECG
PR3	Proteinase 3
PROs	Patient reported outcomes
PRO-C6	Released C-terminal pro-peptide of type VI collagen
QRS	Represents ventricular depolarization on ECG
QT	The duration of ventricular depolarization and repolarization on ECG
QTc	Corrected QT interval
QTcF	QTc by Fridericia's correction method
QTcV	QTc by Van de Water's correction formula
RANTES	Regulated on activation, normal T cell expressed and secreted

RBC	Red blood cell
SAE	Serious adverse event
SAP	Statistical Analysis Plan
SAS	Statistical analysis software
SGRQ-C	St. George's Respiratory Questionnaire compact version
SoA	Schedule of Activities
SOB	Shortness of breath
SOP	Standard operating procedure
SOBQ	Shortness of breath questionnaire
SpO2	Pulse oximetry
SUSAR	Suspected Unexpected Serious Adverse Reaction
TB	Total bilirubin
ug	Microgram
ULN	Upper limit of normal
uM	Micromolar
UPs	Unanticipated problems
VZV	Varicella zoster virus
WBC	White blood cell
Wk.	Week

